## LIST OF ABBREVIATIONS

AASLD	american association for the study of liver diseases
AE	adverse event
ALT	alanine aminotransferase
ANCOVA	analysis of covariance
ATC	anatomical therapeutic chemical
BLOQ	below the limit of quantitation
BMI	body mass index
eHBV	chronic hepatitis B virus infection
CI	confidence interval
CSR	clinical study report
DAIDS	Division of AIDS
DNA	deoxyribonucleic acid
ECG	electrocardiogram
eCRF	case report form
EDC	electronic data capture
EOS	end of study
EOT	end of treatment
ET	early termination
FAS	full Analysis Set
HBcAb	antibody to the HBV core antigen
HBcrAg	hepatitis B core-related antigen
HBeAb	HBeAg antibody
HBeAg	hepatitis B “e” antigen
HBsAb	HBsAg antibody
HBsAg	hepatitis B surface antigen
HBV	hepatitis B virus
HLGT	high-level group term
HLT	high-level term
ID	identification
INR	international normalized ratio
IPD	important protocol deviation(s)
IRT	interactive response technology
LLOQ	lower limit of quantitation
LLT	lower-level term
LOD	limit of detection
LOQ	limit of quantitation
MedDRA	medical dictionary for regulatory activities
NrtI	Nucleos(t)ide reverse transcriptase inhibitor

PD	protocol deviation(s)
PT	preferred term
Q1, Q3	first quartile, third quartile
QD	once daily
RNA	ribonucleic acid
SAE	serious adverse event
SAP	statistical analysis plan
SD	standard deviation
SOC	system organ class
TEAE	treatment-emergent adverse event
TFLs	tables, figures, and listings
TNA	total nucleic acid
ULN	upper limit of normal
VBR	vebicatorvir
WHO	world health organization

## 1. INTRODUCTION

Study ABI-H0731-204 is a randomized Phase 2a, multicenter, open-label, multiple-cohort study evaluating the safety and antiviral activity of Vebicorvir (VBR) and AB-729 in combination with other chronic hepatitis B virus (HBV) infection (cHBV) treatments in subjects with cHBV. The target population is male or female subjects, 18 to 50 years of age, inclusive, with no evidence of cirrhosis or end-stage liver disease. Cohort 1 is prespecified and will enroll virologically-suppressed subjects on nucleos(t)ide reverse transcriptase inhibitor (NrtI) therapy with hepatitis B virus “e” antigen (HBeAg) negative cHBV. Approximately 60 subjects will be enrolled in Cohort 1 of this study. Up to 2 additional cohorts, with approximately 60 subjects per cohort, may be added in future protocol amendments, for a maximum sample size of approximately 180 subjects.

This statistical analysis plan (SAP) describes the statistical analysis methods and data presentations to be used in tables, figures, and listings (TFLs) in the clinical study report (CSR) for Study ABI-H0731-204. This SAP is based on the study protocol Amendment 1, dated 27 October 2021 and the electronic case report form (eCRF). In February 2023, Assembly and Arbutus jointly made the decision to discontinue study ABI-H0731-204, following the observation that AB-729 in dual combination with NrtI alone and as a triple combination with VBR promoted similar on-treatment declines in HBsAg, as has been observed in other AB-729 studies. Thus, there appears to be limited additional benefit to subjects continuing in the post-treatment study period as currently defined in the protocol. The study was prematurely terminated after every active subject completed 48-week treatment period.

The SAP will be finalized before database lock. Only key safety and efficacy endpoints will be performed. Any changes made after the finalization of the SAP will be documented in the Synoptic CSR.

### 1.1. Study Objectives

The primary objective of Cohort 1 is:

- To evaluate the safety and tolerability of combination treatment with VBR, AB-729, and NrtI

The secondary objectives of Cohort 1 are:

- To evaluate the effect of adding VBR and AB-729 to NrtI on reduction in and loss of HBsAg
- To evaluate the effect of adding VBR and AB-729 to NrtI in reducing HBV deoxyribonucleic acid (DNA) levels
- To evaluate the effect of adding VBR and AB-729 to NrtI in reducing HBV ribonucleic acid (RNA) levels

- To evaluate the effect of adding VBR and AB-729 to NrtI in reducing other HBV antigens (ie, hepatitis B core-related antigen [HBcrAg])
- To evaluate the effect of adding VBR and AB-729 to NrtI on hepatitis B surface antigen (HBsAg) seroconversion
- To evaluate the effect of adding VBR and AB-729 to NrtI on normalization of alanine aminotransferase (ALT)
- To evaluate the off-treatment durability of response to treatment with VBR and AB-729
- To evaluate the pharmacokinetics (PK) of VBR and AB-729 when coadministered with NrtI

The exploratory objectives of Cohort 1 are:

[figure not shown]
- To evaluate the emergence of resistance to VBR and AB-729 when coadministered with NrtI
- To evaluate the effect of VBR, AB-729, and NrtI on immunological biomarkers, where applicable
- To evaluate the effect of VBR, AB-729, and NrtI on HBsAg isoforms and immune complexes, where applicable
- To evaluate the effect of AB-729 on an HBV-derived RNA interference biomarker, where applicable

## 1.2. Study Design

This study will assess the safety, antiviral activity, and PK of VBR and AB-729 administered in combination with other cHBV treatments in subjects with cHBV. Cohort 1 is prespecified and will enroll virologically-suppressed subjects on NrtI therapy with HBeAg negative cHBV. Approximately 60 eligible subjects will be randomized 2:1:1 in 1 of 3 treatment groups as shown in

[Figure](#) . Up to 2 additional cohorts may be added in future protocol amendments to evaluate other populations and/or treatment regimens.

**Figure 1-1. Study Design Schematic for Study ABI-H0731-204**

Abbreviations: VBR=vebicorvir; NrtI= nucleos(t)ide /reverse transcriptase inhibitor; Wk=week.

Treatment with VBR and NrtI will be administered orally, once daily; treatment with AB-729 will be administered subcutaneously, once every 8 weeks, for a total of 6 doses. Group 1 will receive VBR+AB-729+NrtI, Group 2 will receive VBR+NrtI, and Group 3 will receive AB-729+NrtI. Treatment assignments will be stratified by HBsAg level (ie, HBsAg  $\leq$ 1000 IU/mL vs  $>$ 1000 IU/mL) during the Screening visit.

### **Treatment Stopping Criteria**

At Week 48, all subjects will have an assessment of Treatment Stopping Criteria. Any subjects who meet the below Treatment Stopping Criteria, will discontinue their assigned treatment including NrtI, and continue with off-treatment follow-up through Week 96, unless they meet the NrtI-restart criteria. Decisions to discontinue assigned treatment and undergo off-treatment follow-up will be based on laboratory results from blood samples collected at the Week 48 visit. Subjects will remain on their assigned oral agents (ie, VBR+NrtI for Groups 1 and 2; NrtI for Group 3) until Week 48 laboratory results required for Treatment Stopping Criteria assessment are available.

Following the announcement of the study early termination in February 2023, Treatment Stopping Criteria were not applicable to the subjects who subsequently reached the Week 48 visit. In this scenario, subjects were to complete the Premature Termination Visit and undergo assessments as outlined in protocol Section 8.5 at the time of the next protocol defined follow up visit. At that time, subjects were to discontinue VBR and study defined NrtI, as applicable, and were to transition to regular standard of care treatment and follow-up outside of the study.

Treatment Stopping Criteria are:

- ALT  $<$  2  $\times$  upper limit of normal (ULN), *and*
- HBV DNA  $<$  lower limit of quantitation (LLOQ), *and*

- HBsAg < 100 IU/mL

Subjects who do not meet the Treatment Stopping Criteria with Week 48 laboratory results will continue treatment with NrtI alone and will remain in follow-up through Week 96.

### **NrtI-Restart Criteria**

Subjects who meet the Treatment Stopping Criteria at the Week 48 assessment but subsequently meet **ANY** of the below NrtI-Restart Criteria, will restart treatment with NrtI and remain in follow-up through Week 96.

NrtI-Restart Criteria are:

- ALT > 10 ×ULN, confirmed by repeat
- ALT > Baseline and > ULN, confirmed by repeat, and
  - Direct bilirubin > 2.0 × ULN, confirmed by repeat, or
  - International Normalized Ratio > 1.5, confirmed by repeat
- ALT ≥ 2 – 5 × ULN AND HBV DNA > 2000 IU/mL for 12 weeks
- ALT elevations ≥ 5 – 10 ×ULN AND HBV DNA > 2000 IU/mL for 4 weeks
- Any clinical decompensation, regardless of HBV DNA level
- Investigator discretion

The schedule of study procedures is presented in tabular form in Tables 9 through 11 of the study protocol.

### **1.3. Sample Size and Power**

Approximately 60 subjects will be randomized in Cohort 1 as shown in [Table 1-2](#). Up to 2 additional cohorts may be subsequently enrolled by future protocol amendments, for a maximum sample size of approximately 180 subjects.

**Table 1-2. Subject Treatment Assignment for Study ABI-H0731-204 Cohort 1**

Treatment Group	Study Treatment	Mode of Delivery	Number of Subjects per Group
1	VBR+AB-729+NrtI	VBR and NrtI: Oral; AB-729: Subcutaneous	30
2	VBR+NrtI	Oral	15
3	AB-729+NrtI	AB-729: Subcutaneous;	15

---

---

NrtI: Oral	
Total Subjects Planned:	60

---

Abbreviations: NrtI=nucleos(t)ide/reverse transcriptase inhibitor; VBR=vebicorvir.

This is a proof-of-concept study. The sample size is similar to that previously utilized for this type of study and is not based upon statistical considerations.

#### **1.4. Methods of Assigning Subjects to Treatment**

##### **1.4.1. Randomization**

All subjects will be assigned a unique Subject identification (ID) at Screening and will be randomized upon successful completion of the Screening assessments. Upon confirmation of subject eligibility on Day 1, an Interactive Response Technology (IRT) system will assign eligible subjects to a study treatment. Additional information on the use of the IRT system is provided in the IRT User Manual.

In Cohort 1, the IRT system will assign eligible subjects in a 2:1:1 ratio to receive either VBR+AB-729+NrtI, VBR+ NrtI, or AB-729+NrtI for 48 weeks. Treatment assignments will be stratified by HBsAg level (ie, HBsAg  $\leq$ 1000 IU/mL vs  $>$ 1000 IU/mL) during the Screening visit.

##### **1.4.2. Blinding**

Not applicable as this is an open-label study.

## **2. TYPE OF PLANNED ANALYSIS**

### **2.1. Interim Analyses**

No formal interim analyses are planned. As an open-label study, the data will be reviewed periodically.

### **2.2. Final Analysis**

As of 14 February 2023, the study was terminated early. The final analysis to support a Synoptic CSR will be performed after all subjects have discontinued or completed the study, outstanding data queries have been resolved or adjudicated as unresolvable, and the data have been cleaned and finalized.

### **3. GENERAL CONSIDERATIONS FOR DATA ANALYSES**

Analysis results will be presented using descriptive statistics. For categorical variables, the number and percentage of subjects in each category will be presented; for continuous variables, the number of subjects (n), mean, standard deviation (SD) or standard error (SE), median, first quartile (Q1), third quartile (Q3), minimum, and maximum will be presented.

No formal statistical testing is planned. Hence no multiplicity adjustment is required.

#### **3.1. Analysis Sets**

Analysis sets define the subjects to be included in an analysis. Analysis sets and their definitions are provided in this section. The analysis set will be identified and included as a subtitle of each table, figure, and listing. For each analysis set, the number and percentage of subjects eligible for inclusion will be summarized by treatment group. A listing of reasons for exclusion from analysis sets will be provided by subject.

##### **3.1.1. All Randomized Analysis Set**

All Randomized Analysis Set includes all subjects who were randomized in the study, classified according to the treatment group into which they were randomized regardless of the actual treatment received.

##### **3.1.2. Full Analysis Set**

The Full Analysis Set (FAS) includes all randomized subjects, classified according to the treatment group into which they were randomized regardless of the actual treatment received who took at least 1 dose of a study drug. This is the primary analysis set for efficacy analyses.

##### **3.1.3. Safety Analysis Set**

The Safety Analysis Set includes all subjects, classified according to the actual treatment received regardless of random assignment, who took at least 1 dose of a study drug. This is the primary analysis set for safety analyses.

#### **3.2. Subject Grouping**

For analyses based on the All Randomized Analysis Set and FAS, subjects will be grouped according to the treatment to which they were randomized. For analyses based on the Safety Analysis Set, subjects will be grouped according to the actual treatment received. The actual treatment received will differ from the randomized treatment only when their actual treatment differs from randomized treatment for the entire treatment duration.

### 3.3. Strata and Covariates

Subjects will be randomly assigned to treatment groups via an IRT system in a 2:1:1 ratio to receive either VBR+AB-729+NrtI, VBR+NrtI, or AB-729+NrtI using a stratified randomization schedule. Stratification will be by HBsAg level (ie, HBsAg  $\leq$ 1000 IU/mL vs  $>$ 1000 IU/mL) during the Screening visit.

If there are discrepancies in stratification factor values between the IRT and the clinical database, the values recorded in the clinical database will be used for analyses. Given that the study is early terminated, a sensitivity analysis of the efficacy endpoints will not be performed for the stratification discrepancy.

### 3.4. Data Handling Conventions and Transformations

Subject age collected at Screening visit will be used for analyses and presented in listings. The age is derived in the electronic data capture (EDC) system based on year of birth and informed consent date.

Laboratory data that are continuous in nature but are less than the lower limit of quantitation (LLOQ), less than the limit of detection (LOD), or above the upper limit of quantitation (LOQ) will be imputed for the purposes of calculating descriptive statistics.

A value that is half of the LLOQ will be used to calculate descriptive statistics if the datum is reported in the form of  $<x$  or  $\leq x$  (where  $x$  is considered the LLOQ or LOD), or is reported as not detected. For example, if the reported datum is " $<10$ ", then a value of 5 will be assigned. If the LLOQ is reported in log units, the imputed value will be half of the equivalent non-log LLOQ value.

A value that is 1 significant value unit above the upper LOQ will be used to calculate descriptive statistics if the datum is reported in the form of " $> x$ " (where  $x$  is considered the LOQ). For example, if the result of a continuous laboratory test is  $>20$ , a value of 21 will be assigned. If the result of a continuous laboratory test is  $>20.1$ , a value of 20.2 will be assigned.

The LOQ will be used to calculate descriptive statistics if the datum is reported in the form of " $\geq x$ " (where  $x$  is considered the LOQ).

For selected analyses, virology efficacy data will be transformed to the logarithmic (base 10) scale.

Total bilirubin values entered as  $< 0.2$  mg/dL will be analyzed as 0.1 mg/dL; direct bilirubin values entered as  $< 0.1$  mg/dL will be analyzed as 0.05 mg/dL (according to the methods of Nehls and Akland, 1973).

### **3.5. Missing Data and Outliers**

#### **3.5.1. Missing Data**

In general, missing data will not be imputed unless methods for handling missing data are specified. Exceptions are presented in this document.

For missing last dose date of study drug, imputation rules are described in [Section 4.2.1](#). The handling of missing or incomplete dates for adverse event (AE) onset is described in [Section 7.1.5.2](#), and for prior and concomitant medications in [Section 7.3.2](#).

#### **3.5.2. Outliers**

Outliers will be identified during the data management review process. No sensitivity analyses will be conducted. All data will be included in the data analysis.

### **3.6. Analytic Definitions**

#### **3.6.1. Definition of Study Drug**

In this study, study drug is defined as VBR and AB-729.

#### **3.6.2. Definition of Baseline**

In general, Baseline will be defined as the last non-missing evaluation prior to the first dose on Day 1. Change from Baseline will be defined as the result at desired timepoint minus the result at Baseline.

#### **3.6.3. Definition of Study Phase and End of Study**

The analyses will include all the data collected in this study based on three phases defined as follows.

- **On-Treatment Phase:** when a subject is undergoing treatment with AB-729, VBR, or both per treatment group (ie, from first dose of either study drug through the last dose of VBR +1 day or last dose of AB-729 +56 days, whichever is later)
- **Off-Treatment Phase:** after a subject has discontinued AB-729, VBR, or both per treatment group, and prior to NrtI restart if applicable (ie, after the last dose of VBR +1 day or last dose of AB-729 +56 days, whichever is later, until the end of study or before the first dose of NrtI if it was restarted)
- **NrtI-Restart Phase:** after a subject has restarted NrtI, following the Off-Treatment Phase (ie, from the first dose of restarted NrtI through the end of study)

End of study is defined as when the last subject completes the last follow-up or is considered “lost to follow-up”, whichever is later.

Subjects may prematurely discontinue study drug earlier prior to the Week 48 visit. The end dates of the On-Treatment Phase may vary for individual subjects based on their last dose dates as defined in [Section 3.6.3](#).

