#### **3.6.4. Definition of Study Day**

The first dose date of VBR and of AB-729 will be calculated where applicable. Study Day 1 is defined as the first dose date of study drug, which is the minimum of the first dose dates of VBR and of AB-729 in a treatment group. If the first dose date is missing, the date of randomization will be used.

The last dose date of VBR and of AB-729 will be calculated where applicable. The last dose date of each drug will be the end date on the respective study drug end of treatment eCRF. The last dose date of study drug will be defined as the maximum of the last dose dates of VBR and of AB-729 in a treatment group.

For the On-Treatment Phase, study day will be calculated from Study Day 1 and derived as follows:

- For days prior to the first dose: Assessment Date – Study Day 1
- For postdose study days: Assessment Date – Study Day 1 + 1

For the Off-Treatment Phase, the Off-Treatment Day 1 will be defined as the day after the last dose date of study drug VBR or 56 days after last dose of AB-729, whichever is later. The off-treatment study day will be calculated from the last dose date and derived as Assessment Date – Off-Treatment Day 1 + 1.

For the NrtI-Restart Phase, the NrtI-Restart Day 1 will be defined as the first dose date of restarted NrtI. The NrtI-Restart study day will be calculated from the first dose of NrtI and derived as Assessment Date – First Dose Date of NrtI + 1.

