#### **3.6.5. Analysis Visit Windows**

Subject visits might not occur on protocol-specified days. Therefore, for the purpose of analysis, observations will be assigned to analysis windows. For the On-Treatment Phase, data will be summarized up to Week 48 visit or premature termination visit. For the Off-Treatment Phase, the data will be summarized by treatment action up to the end of study, or up to NrtI restart for applicable patients. For the NrtI-Restart Phase, data will be summarized only for applicable subjects who restarted NrtI after having discontinued AB-729, VBR, or both.

The analysis windows for the On-Treatment Phase assessments of HBV TNA, HBV RNA, HBsAg, Vital signs, Chemistry, Hematology, Coagulation, and Urinalysis are provided in [Table 3-1](#).

For the On-Treatment Phase assessments of HBeAg, only the analysis visits of Baseline and Week 48 will be presented in the summary tables. Any non-baseline on-treatment visit will be categorized under analysis visit Week 48.

**Table 3-1 On-Treatment Phase Analysis Visit Windows for Efficacy (HBV TNA, HBV RNA, HBsAg), Vital Signs, and Laboratory Assessments**

Nominal Visit	On-Treatment Phase Nominal Study Day	Visit Window Study Day	
		Lower Limit	Upper Limit
Baseline	1	(none)	1
Week 2	14	2	21
Week 4	28	22	42
Week 8	56	43	70
Week 12	84	71	98
Week 16	112	99	126
Week 20	140	127	154
Week 24	168	155	182
Week 28	196	183	210
Week 32	224	211	238
Week 36	252	239	266
Week 40	280	267	294
Week 44	308	295	322
Week 48	336	323	350
Week 52	364	351	378
Week 56	392	379	≥392

The analysis windows for the On-Treatment Phase assessments of HBV DNA, HBcrAg, and electrocardiogram (ECG) are provided in [Table 3-2](#).

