The proportion of subjects meeting treatment stopping criteria will be summarized. A by-subject listing detailing each subject's treatment stopping decision and the HBV DNA, HBsAg, and ALT results from their last on-treatment (i.e. week 48) study visit will be included.

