#### **6.1.2. Analysis Methods for Efficacy Endpoints**

The observed and mean change in  $\log_{10}$  HBV RNA, HBV TNA, HBsAg, HBcrAg, and ALT from Baseline will be summarized using descriptive statistics (sample size, mean, SD, median, Q1, Q3, minimum, and maximum) by phase, treatment group, and treatment action at each visit.

For the On-Treatment Phase, analysis will be performed to compare the mean changes of  $\log_{10}$  HBV RNA,  $\log_{10}$  HBV TNA,  $\log_{10}$  HBsAg,  $\log_{10}$  HBcrAg, and ALT from Baseline to each timepoint between VBR+AB-729+NrtI and VBR+NrtI, and between VBR+AB-729+NrtI and AB-729+NrtI. The primary comparison for mean change endpoints will be made using an analysis of covariance (ANCOVA) model, including baseline value, the stratification factors, and treatment group as covariates. The estimated least square means of treatment effects and estimated difference in treatment effects between treatment groups at Week 48 will be presented along with the 95% CIs and p-values. The analysis will be based on observed data.

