#### **7.2.1.2. Summaries of Laboratory Abnormalities**

A summary (number and percentage of subjects) for treatment-emergent laboratory abnormalities will be provided by lab test and treatment group; subjects will be categorized according to the most severe postbaseline abnormality grade for a given laboratory test.

Treatment-emergent lab abnormalities will be summarized based on the Safety Analysis Set. Tables will be created per study phase (i.e. On-Treatment Phase, Off-Treatment Phase, and NrtI-Restart Phase).

For all summaries of laboratory abnormalities, the denominator is the number of subjects with nonmissing postbaseline values in each phase.

The maximum post-baseline grade in each phase will be tabulated for each laboratory test, and percentages will be based on the number of subjects with a post-baseline evaluation of the specific laboratory test. The laboratory abnormalities during the follow-up period will also be summarized.

A by-subject listing of graded laboratory abnormalities will be provided by subject ID number and visit in chronological order. This listing will include all test results that were collected throughout the study for the lab test of interest, with all applicable severity grades displayed.

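### SAP 3.6.3 ends Group 3's On-Treatment Phase exactly on the nominal Week 48 day, so a literal derivation can reclassify a protocol-compliant Week 48 sample as Off-Treatment

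*Combined protocol and SAP*

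**What the plan says.** SAP 3.6.3 defines the On-Treatment Phase from the first dose of either study drug "through the last dose of VBR +1 day or last dose of AB-729 +56 days, whichever is later". SAP 3.6.1 limits study drug to VBR and AB-729, so continuing NrtI does not prolong the phase. SAP 3.6.3 closes with a remark on early discontinuation and adds: "The end dates of the On-Treatment Phase may vary for individual subjects based on their last dose dates".

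Other places treat Week 48 as on-treatment:
- Protocol Table 9, the on-treatment schedule for all subjects, includes Week 48 with a ±3-day window.
- SAP 3.6.5 says: "For the On-Treatment Phase, data will be summarized up to Week 48 visit or premature termination visit". Table 3-1 gives Week 48 the window of Study Days 323 to 350, and Table 3-2 leaves its Week 48 window open above.
- SAP 4.1 plans a listing in which "HBV DNA, HBsAg, and ALT results from their last on-treatment (i.e. week 48) study visit will be included".
- SAP 6.1.2 begins "For the On-Treatment Phase, analysis will be performed to compare the mean changes of" and presents the estimated group differences at Week 48, on observed data.

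SAP 3.6.4 sets Off-Treatment Day 1 as "the day after the last dose date of study drug VBR or 56 days after last dose of AB-729, whichever is later", and takes last dose dates from a form: "The last dose date of each drug will be the end date on the respective study drug end of treatment eCRF".

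**The concern.** The phase has to be assigned before the visit window. The window tables are specific to a phase, and off-treatment days are counted from a different origin. A programmer who derives phase from the 3.6.3 dates will therefore settle the status of a late Week 48 sample before Table 3-1 is consulted.

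Two kinds of subject are governed only by the AB-729 part of the rule. The first is all of Group 3. The second is a narrow Group 1 case in protocol 7.1: NrtI is stopped, VBR must stop with it, AB-729 continues through Week 40, and scheduled visits go on as planned.

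Group 1 versus Group 3 is the comparison that isolates what VBR adds. If Group 3 samples drop out of it at Week 48, the group's n depends on visit timing and on how the phase was coded. HBcrAg is the most exposed variable, because Week 48 is its only scheduled post-baseline on-treatment sample. Laboratory results are affected too. SAP 7.2.1.2 states "The maximum post-baseline grade in each phase will be tabulated for each laboratory test", so an abnormality in a displaced sample would be counted as Off-Treatment. Early termination does not remove the point, since SAP section 1 says every active subject completed the 48-week treatment period.

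**Working it through.** **Inputs.** Last AB-729 dose at Week 40, nominal Study Day 280; Week 48 nominal Study Day 336, window 323 to 350 (protocol 8.3.3; SAP Table 3-1). Visit window ±3 days at both visits (protocol Table 9). Planned group sizes 30, 15 and 15 (protocol Table 7).

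**Step 1: the plan's own figure.** 280 + 56 = 336. The phase limit coincides with nominal Week 48 and leaves no margin.

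**Step 2: compliant gaps.** Gap = 56 + (Week 48 offset) − (Week 40 offset), each offset from −3 to +3. The range is 56 − 6 = 50 to 56 + 6 = 62 days. Of the 7 × 7 = 49 offset pairs, 21 exceed 56 days, 7 equal it and 21 fall below it. Every compliant Week 48 visit lies on Study Days 333 to 339, inside 323 to 350.

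**Step 3: where a displaced sample goes.** Off-treatment day = assessment date − Off-Treatment Day 1 + 1. The wording of 3.6.4 allows Day 1 to be dose + 56 or dose + 57, so days 57 to 62 become off-treatment days 2 to 7 or 1 to 6. For HBsAg, HBV RNA and HBV TNA, days 2 to 42 form Off-Treatment Week 4 (nominal day 28). A sample on days 2 to 7 is 26 to 21 days from nominal. A Week 52 visit (364 ± 5), with the Week 40 dose on day 277, 280 or 283, is 1 to 9 days away in the cases run. The closest-record rule in 3.6.6 then picks Week 52, so the Week 48 value can leave both the ANCOVA and the by-visit summary. It stays in the database.

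**Step 4: size.** The documents give no visit dates, so this is a range. If a share f of visits falls on the nominal day and the rest spreads evenly over the other six days, P(equal offsets) = f² + (1 − f)²/6 and P(gap > 56) = (1 − P(equal))/2.
- f = 0.90: P(equal) = 0.8117; (1 − 0.8117)/2 = 0.094.
- f = 0.70: P(equal) = 0.505; (1 − 0.505)/2 = 0.248.
- Independent uniform offsets, illustrative only: 21/49 = 0.429.

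SE ratio for Group 1 versus Group 3 = √(1/30 + 1/n₃) / √(1/30 + 1/15). Half-width = t(0.975, N − 5) × SD × √(1/30 + 1/n₃), with N = 45 + n₃, five model parameters, balanced covariates and an assumed HBsAg residual SD of 0.45 log₁₀.

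| Timing | Lost of 15 | n₃ | SE ratio | 95% half-width |
|---|---|---|---|---|
| Exact 56-day spacing | 0 | 15 | 1.000 | ±0.285 |
| One displaced sample | 1 (6.7%) | 14 | 1.024 | ±0.292 |
| 90% on nominal day | 1.4 (9%) | 13.6 | 1.034 | ±0.295 |
| 70% on nominal day | 3.7 (25%) | 11.3 | 1.104 | ±0.315 |
| Uniform (illustrative) | 6.4 (43%) | 8.57 | 1.225 | ±0.350 |

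The SD is bracketed by Week 12 SEMs from cohorts of six (protocol 2.3.3.3): 0.154 × √6 = 0.377 and 0.238 × √6 = 0.583. From no loss to 43% loss, the half-width runs from ±0.24 to ±0.29 at the lower SD and from ±0.37 to ±0.45 at the upper. These cohorts had other dosing schedules and a Week 12 endpoint, so they give only an order of magnitude.

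**Step 5: who is not exposed.** Subjects still on VBR in Groups 1 and 2 take it until Week 48 results arrive (protocol 4.1.1) or, after the February 2023 termination, until the next follow-up visit (SAP 1.2). Their last VBR dose + 1 day is later than Week 48.

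**The case against.** The strongest reply is that the intended reading is plain. Protocol Table 9, SAP 3.6.5, both window tables, 4.1 and 6.1.2 all place Week 48 on treatment, and 3.6.5 introduces windows precisely because visits slip. That stands. A reader might infer that the SAP leaves the status of Week 48 open; it does not. What is missing is a phase rule that delivers the intent.

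A reader might also take "The end dates of the On-Treatment Phase may vary for individual subjects based on their last dose dates" as a general rule overriding 3.6.5. The sentence before it concerns subjects who stop study drug before Week 48, so it does not clearly reach completers with a slightly late visit.

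Nor does protocol 7.1 cover every Group 1 subject who stops VBR early. Scheduled visits continue only where VBR stopped because NrtI stopped; other early discontinuers have a Premature Termination visit and move to the follow-up schedule.

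Section 3.6.4 can be defended as numbering days rather than assigning phase, with Off-Treatment Day 1 serving as an anchor record, since its window has no lower limit. Even so, last VBR dose + 1 day is On-Treatment in 3.6.3 and Off-Treatment Day 1 in 3.6.4, and one definition should serve both.

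Finally, the stakes are modest. SAP section 3 plans no formal testing, only a Synoptic CSR follows, and displaced laboratory abnormalities would still be tabulated and listed, though under another phase.

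**Conclusion.** The point holds as a defect in the phase derivation. The date rule in 3.6.3, applied as written, can move a compliant Group 3 Week 48 sample into the Off-Treatment Phase, against the evident intent of the protocol and the rest of the SAP. The same applies to the narrow Group 1 case.

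The consequence is a possible loss of precision and an n that depends on coding. It may be zero; one displaced sample costs about 2% in standard error. The 43% figure should not be read as an expected loss, because nothing in the documents supports uniform visit timing. A reader might also infer bias from the fact that only Group 3 is broadly exposed, but no link between visit timing and outcome is shown. Comparisons through Week 44 are unaffected.

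The conclusion assumes that the AB-729 end date on the end-of-treatment eCRF is the Week 40 injection date; that form is not among the documents. Severity is minor to should-fix: the effect is small or unknown, but the repair is cheap.

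**What to change.** In SAP 3.6.3, end the On-Treatment Phase at the latest of:
- last VBR dose + 1 day;
- last AB-729 dose + 56 days;
- for subjects who received the Week 40 AB-729 injection, the Week 48 visit date, provided it falls within the Table 3-1 Week 48 window (Study Days 323 to 350).

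If there is no Week 48 visit in that window, the existing dose-date rule stands. The upper bound stops a very late visit from stretching the phase into the Week 52 or Week 56 window.

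In SAP 3.6.4, define Off-Treatment Day 1 as the day after the On-Treatment Phase ends, which removes the one-day overlap.

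If the SAP is already final, record the change in the Synoptic CSR, as SAP section 1 provides. The cost is two sentences and one derivation in the analysis dataset, with no new data. It changes analysis-phase assignment only, not treatment.
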